## Statistical Analysis Plan

Imputation will be performed using multiple imputation by fully conditional specification (Van Buuren, 2007), with the number of imputations equal to the percentage of missing data.

- Number of days between platelet count first  $30 \times 10^9/L$  or below OR if the participant was admitted with a platelet count already below  $30 \times 10^9/L$ , number of days between the start of chemotherapy or conditioning for a stem cell transplant, and start of trial treatment, or planned start for those participants who did not receive treatment, will be summarised by treatment arm, for all participants included in the mITT analysis. It is important to monitor this since the 30-day analysis period only begins at the start of study treatment.
- Number of bleeds between platelet count first  $30 \times 10^9/L$  or below and start of trial treatment or planned start for those participants who did not receive treatment will be summarised by treatment arm, for all participants included in the mITT analysis. It is important to monitor whether any bleeds occurred prior to the start of the 30-day analysis period.

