## Statistical Analysis Plan

---

excellent. A bleeding assessment was completed on 93% (8405/9030) of days for participants in the no-prophylaxis group, and 97% (8733/8970) of days in the prophylaxis group. The majority of participants in both arms had bleeding information completed on each trial day (median no-prophylaxis 30 days (IQR 29 to 30); median prophylaxis 30 days (IQR 30 to 30)). There were also only 6 deaths (1% of participants) while on the trial.

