### 4.7 Sensitivity analyses

- The key demographics and clinical condition of participants at consent will be described for each arm of the trial, comparing all randomised participants with the mITT population to ensure that excluded participants are similar across the arms.
- Per-protocol analysis of the primary outcome. This analysis will exclude all participants who did not adhere to a set of minimum protocol-adherence criteria during the first 30 days of the trial. Participants who were randomised in error will be excluded from this analysis. The per-protocol analysis will be performed using the same method as for the mITT analysis. Protocol-adherence will be summarised by treatment arm. In addition, since the per-protocol analysis may lead to an over-estimation of the difference in the proportion experiencing the primary outcome in each treatment arm, which may be explained by differing levels of protocol-adherence in each treatment arm, an instrumental variable analysis will be performed. The randomisation arm will be used as the instrument. The instrumental variable estimate will be calculated as the mITT estimate of the difference in the proportion experiencing the primary outcome in each treatment arm / proportion adhering to the minimum compliance criteria in the active treatment arm. The standard error of the instrumental variable estimate will be calculated using two-stage least squares.
- Some participants may withdraw or be lost to follow up during the conduct of the trial. In addition, some participants who are followed up for the full 30 days may be missing some bleeding assessments. In these cases, it is impossible to know whether such participants would be either less or more likely to experience bleeding if they had complete bleeding assessments for the full 30-day follow up period. Sensitivity of the primary outcome to incomplete follow up and missing bleeding assessments will be assessed by re-calculating the primary outcome, by arm, for all participants included in the mITT analysis, after imputing all missing bleeding assessments up to study day 30.

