### 5.4 Primary Outcome table(s)

**Table xx Primary outcome table**

	Active arm (n=)	Placebo arm (n=)	Overall (n=)	P value
Proportion of participants who die or have bleeding of WHO grade 2 or above from day 1 up to study day 30 - % (95% CI)				
Hazard ratio (95% CI)				
Risk difference (95% CI)				
Number needed to treat  – N				
Proportion of missing bleeding assessments from day 1 up to study day 30 – n/N (%)				
Proportion of participants missing vital status at study day 30 – n/N (%)				
All primary outcome analyses are adjusted for centre.				
 For benefit. Calculated as 1/risk difference.				

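### The rule for the number of imputations has no minimum, no seed and no defined percentage; at the earlier trial's missingness it gives about 3 to 7, enough for the seed to move a borderline p-value across 0.05

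*SAP*

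**What the plan says.** The main analysis of the primary outcome (SAP 4.3 and 4.8) counts any missed bleeding assessment, up to day 30 or last contact, as grade 1 or below. SAP 4.7 checks this by recalculating the primary outcome in the mITT population "after imputing all missing bleeding assessments up to study day 30". The method is fully conditional specification, "with the number of imputations equal to the percentage of missing data". SAP 4.8 refers back to this analysis as the test of sensitivity to missing data.

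The SAP gives no lower limit, rounding rule or seed for the imputations. It does not say whether the percentage is of assessments or of participants with any gap, or whether it is taken per arm or overall. The primary outcome table in SAP 5.4 does have a row headed "Proportion of missing bleeding assessments from day 1 up to study day 30".

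The SAP projects no missingness rate for this trial. Its only figures are those achieved in the earlier platelet-prophylaxis trial (SAP 1.5.2): "A bleeding assessment was completed on 93% (8405/9030) of days for participants in the no-prophylaxis group, and 97% (8733/8970) of days" in the prophylaxis group.

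**The concern.** Multiple imputation draws missing values at random, so its pooled estimate, standard error and p-value carry Monte Carlo error that shrinks as the number of imputations, m, grows. Linking m to a small percentage makes m small, and without a seed the particular draw is not fixed in advance.

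This is the only planned analysis that tests the rule treating missing assessments as grade 1 or below. Its table in SAP 5.9 reports a hazard ratio, a risk difference and a p-value, and SAP 4.2 takes p below 0.05 as evidence of a difference. If the result is borderline, the choice of seed could settle whether the primary finding is described as robust to missing data.

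**Working it through.** **Step 1: completeness figures (SAP 1.5.2).** 8405/9030 = 93.1% and 8733/8970 = 97.4%, so the stated 93% and 97% reproduce. Missing days are 9030 − 8405 = 625 (6.92%) and 8970 − 8733 = 237 (2.64%). Pooled, 862/18000 = 4.79%.

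The denominators are 301 × 30 and 299 × 30, the numbers randomised given in protocol 1.2. Days lost to withdrawal are therefore already counted. So are days after death, which need no imputation, but with 6 deaths these are at most 180 days. Removing them all gives (862 − 180)/(18000 − 180) = 3.8%, or m = 4 instead of 5.

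**Step 2: what the rule yields.**
- Percentage of assessments: m = 3, 5 or 7 at 2.64%, 4.79% or 6.92%. This is the natural reading, because assessments are what is imputed and what SAP 5.4 tabulates.
- Percentage of participants with any gap: the lower quartile in the earlier trial's no-prophylaxis group was 29 of 30 days, so at least about a quarter of that group had a gap and m would be at least about 25.

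**Step 3: Monte Carlo error by formula.** With FMI the fraction of missing information, the Monte Carlo SD of the pooled estimate, as a share of its standard error, is √[FMI/((1 + 1/m)m)] = √[FMI/(m + 1)]. This is also the SD on the z scale. FMI is set to the percentage missing, an assumption that step 4 checks.

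| Missing days | m by the rule | Share of SE, m by the rule | Share of SE, m = 50 | Ratio |
|---|---|---|---|---|
| 2.64% | 3 | √(0.0264/4) = 0.081 | √(0.0264/51) = 0.023 | 3.6 |
| 4.79% | 5 | √(0.0479/6) = 0.089 | √(0.0479/51) = 0.031 | 2.9 |
| 6.92% | 7 | √(0.0692/8) = 0.093 | √(0.0692/51) = 0.037 | 2.5 |

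For a limiting p of 0.055 (z = 1.919) at 4.79% missing, z ± 1.96 × 0.089 gives p from 0.036 to 0.081 at m = 5. At m = 50, z ± 1.96 × 0.031 gives 0.048 to 0.063. The formula ignores noise in the between-imputation variance, so the true ranges are somewhat wider.

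**Step 4: simulation.** One data set with 293 participants per arm (586 in total, SAP 1.5.2) was fixed and m imputations were drawn repeatedly, pooling the risk difference by Rubin's rules. Assumptions not in the documents: constant daily hazard, missingness unrelated to bleeding, a 30% daily chance of repeat bleeding after a first bleed, no site effect, and missing days either scattered or caused by withdrawal at a uniformly distributed time.

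- FMI was about 2% to 9%, close to the percentage missing.
- With m set by the rule, the Monte Carlo SD was about 8% to 11% of the standard error, or 0.3 to 0.5 percentage points on a risk difference with a standard error of about 4.1 points. At m = 50 it was about 2% to 4%.
- Design effect (43% against 32%, limiting p about 0.006): p ranged over seeds from about 0.003 to 0.016 and was below 0.05 in essentially every run.
- Borderline effect at 4.79% missing (95% range of p over seeds):

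| Pattern | Limiting p | m = 5 | m = 50 |
|---|---|---|---|
| Scattered days | 0.058 | 0.034 to 0.102 | 0.049 to 0.069 |
| Withdrawal | 0.054 | 0.033 to 0.089 | 0.046 to 0.062 |

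At m = 5, p fell below 0.05 in 27% (scattered) and 36% (withdrawal) of runs. At m = 50 these were 4% and 18%.

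**The case against.** The strongest defence is that the rule scales itself. If FMI is close to the percentage missing, m = 100 × FMI and Monte Carlo error stays near √(FMI/m) = 10% of the standard error at any level of missingness, with relative efficiency of about 1/(1 + 0.01) = 0.99. A sensitivity analysis is read mainly for consistency of the estimate, and a shift of a tenth of a standard error does not change that reading. The main analysis fills gaps without random draws, and SAP 4.8 and 5.4 require missingness to be reported by arm. All of this stands, and it is why the point is minor.

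Three stronger readings are tempting, and the documents do not support them:

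- A reader might infer that m could be 1, leaving between-imputation variance inestimable. That needs missingness of about 1.5% or less, below both of the earlier trial's figures. The case shows why a minimum is useful but is not the expected outcome.
- A reader might infer that the percentage of missing days badly understates the information lost, because many more participants than days are affected. In the simulation FMI stayed near the percentage of days. Pairing m = 3 with an FMI of 20% would give √(0.20/4) = 0.22 on the z scale, but m = 3 arises at about 2.6% missing, where the matched value is about 0.08.
- A reader might infer that the sensitivity result depends on the seed in general. It does so only when the limiting p is already close to 0.05.

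**Conclusion.** The point holds as a specification gap with a small effect. Three to seven imputations is conditional: it assumes the per-assessment reading and missingness like the earlier trial's, which the SAP reports but does not project for this one. The participant reading would give a much larger m, and a rule that allows either is itself under-specified.

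On the per-assessment reading the cost is Monte Carlo error of roughly a tenth of a standard error. That does not matter at the design effect, but it is enough for the seed to decide which side of 0.05 a borderline result falls on. The p-value ranges also rest on the simulation assumptions listed above. Nothing here touches the primary analysis or its missing-data rule. It is a free improvement of minor severity.

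**What to change.** In SAP 4.7, replace the rule with a fixed minimum: at least 50 imputations, or the larger of 50 and the percentage of participants with any missing assessment. Pre-specify the seed, and report the Monte Carlo error beside the pooled estimate and p-value. If a percentage is kept in the rule, state its denominator and whether it is taken overall or per arm.

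At the earlier trial's missingness, 50 imputations cut the Monte Carlo SD by a factor of about 2.5 to 3.6 (step 3). A p-value very close to 0.05 can still cross it at 50, which is why the Monte Carlo error should be reported as well. The cost is a short SAP edit and computing time; no data collection or sample-size change is needed.

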### 4.8 Procedures for handling Missing Data

For all outcomes, the volume of missing data will be summarised by treatment arm.

Participants withdrawn or lost to follow up before day 30 will be included in the primary outcome analysis (and in secondary outcome analyses where possible), censoring at the time that they withdrew/were lost to follow up.

It is expected that deaths and other safety outcomes, other than for participants withdrawn or lost to follow up, will be fully reported.

For the main analysis of the primary outcome, any missing bleeding assessments during the 30-day follow up period or to the last point of contact, whichever is first, will be assumed to be grade 1 or below. Sensitivity of the primary outcome to missing data will be assessed as per the sensitivity analysis described above.

Missing values for secondary and baseline characteristics will not be imputed. Missing data will be excluded from the relevant analyses.

### 5. Data Analysis Tables to be Completed

Data analysis will be based on the following tables.

#### 5.1 Interim analysis tables

**Table 1 Baseline characteristics for UK vs. Australian participants – data are number (%) for categorical variables, and mean (SD) for continuous variables**

	UK (n=)	Australia (n=)	P value
Sex: Male			
Diagnosis: Acute leukaemia			
Treatment plan: Autograft			
Haemoglobin at randomisation (G/L)			

'Other' diagnosis includes xxx and 'other' treatment plan includes xxx.

Sex is missing for xxx participants, of which xxx are not available.

Diagnosis is missing for xxx participants, of which xxx are not available.

Treatment plan is missing for xxx participants, of which xxx are not available.

Haemoglobin at randomisation is missing for xxx participants, of which xxx are not available.

## Statistical Analysis Plan

---

**Table 2 Safety data summary - data are numbers**

Outcome	Arm A (n=)	Arm B (n=)	Overall (n=)
Total number of serious adverse events (SAE) up to day 60			
Sepsis			
Organ failure			
GvHD			
Transfusion reaction			
Fever			
Other SAEs			
Number of participants experiencing at least one SAE			
Symptomatic thrombotic events up to day 120			
Venous thromboembolisms			
Arterial ischaemic events			
Veno-occlusive disease up to day 120			
Unexpected adverse reactions up to day 60			
Deaths up to day 120			

## Statistical Analysis Plan

---

## Statistical Analysis Plan

---

### 5.2.2 Participants withdrawn

**Table xx Participants withdrawn**

Participant ID	Arm	Reason for withdrawal	Stage of withdrawal

### 5.2.3 Participants randomised in error

**Table xx Participants randomised in error**

Participant ID	Arm	Detail of error

### 5.2.4 Participants entered in trial more than once (if relevant) or co-enrolled in other trials

**Table xx Participants co-enrolled in other trials**

Participant ID	Arm	Detail of co-enrolment

### 5.2.5 Protocol Deviations

**Table xx Protocol deviations**

Participant ID	Arm	Detail of protocol deviation

### 5.3 Baseline Characteristics tables

**Table xx Baseline characteristics- data are number (%) for categorical variables, and mean (SD) for continuous variables**

	Active arm (n=)	Placebo arm (n=)	Overall (n=)

## Statistical Analysis Plan

Male			
Age (years)			
Ethnicity			
White			
Asian			
Black African			
Black Caribbean			
Arab/other Middle East ancestry			
Aboriginal			
Other			
Mixed ethnic group:			
White/Black Caribbean			
White/Black African			
White/Asian			
White/Aboriginal			
White/Other			
Other mixed ethnic group			
Height (cm)			
Weight (kg)			
Diagnosis			
AML			
ALL			
APL			
CML			
CLL			
Hodgkins Lymphoma			
Non-Hodgkins Lymphoma			
Myeloma			
MDS			
Other			
Treatment plan			
Induction chemotherapy			
Consolidation chemotherapy			
Autograft			
Allograft			
Other			
Platelet count at consent ( $\times 10^9/L$ )			
Platelet count at randomisation ( $\times 10^9/L$ )			
Haemoglobin at consent (G/L)			
Haemoglobin at randomisation (G/L)			
FACT-G subscale score at randomisation			
Physical well-being			
Social/family well-being			
Emotional well-being			
Functional well-being			
FACT-G total score at randomisation			

## Statistical Analysis Plan

FACT-Th total score at randomisation			
Medical history			
Diabetes requiring treatment			
Hypertension requiring treatment			
Renal impairment requiring treatment			
Confirmed invasive fungal infection			
Other malignancy			
HLA antibodies			

'Other' diagnoses were xxx and 'other' treatment plans were xxx.

### 5.4 Primary Outcome table(s)

**Table xx Primary outcome table**

	Active arm (n=)	Placebo arm (n=)	Overall (n=)	P value
Proportion of participants who die or have bleeding of WHO grade 2 or above from day 1 up to study day 30 - % (95% CI)				
Hazard ratio (95% CI)				
Risk difference (95% CI)				
Number needed to treat  – N				
Proportion of missing bleeding assessments from day 1 up to study day 30 – n/N (%)				
Proportion of participants missing vital status at study day 30 – n/N (%)				
All primary outcome analyses are adjusted for centre.				
 For benefit. Calculated as 1/risk difference.				

### 5.5 Secondary Outcome table(s)

**Table xx Secondary efficacy outcomes table**

Outcome	Active arm (n=)	Placebo arm (n=)	Overall (n=)	P value
Proportion of days with WHO grade 2 bleeding or above – % (95% CI)				
Odds ratio  (95% CI)				

## Statistical Analysis Plan

Time to first episode of bleeding of WHO grade 2 or greater (days) (median, IQR^2)				
Hazard ratio (95% CI)				
Highest grade of bleeding a participant experiences				
Grade 0 – n/N (%)				
Grade 1 – n/N (%)				
Grade 2 – n/N (%)				
Grade 3 – n/N (%)				
Grade 4 – n/N (%)				
Grade unassigned – n/N (%)				
Proportional odds ratio (95% CI)				
Grades 2, 3 or 4 – n/N (%)				
Number of platelet transfusions/participant (units) up to study day 30 (median, IQR)				
Rate ratio (95% CI)				
Number of red cell transfusions/participant (units) up to study day 30 (median, IQR)				
Rate ratio (95% CI)				
Proportion of participants surviving up to 30 days without a platelet transfusion – % (95% CI)				
Hazard ratio (95% CI)				
Proportion of participants surviving up to 30 days without a red cell transfusion – % (95% CI)				
Hazard ratio (95% CI)				
All secondary efficacy outcome analyses are adjusted for centre.				
 Odds ratio from logistic regression model, also adjusted for participant.				
 Lower quartile will be reported. Median and upper quartile will be reported if achieved.				

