6.4.2. Red Cell Transfusions

As a low haematocrit has been associated with an increased bleeding risk (36-38) a common policy to guide red cell transfusion support according to the BCSH Guidelines (UK) and in Australia the national Patient Blood Management Guidelines will be followed, available at <https://www.blood.gov.au/pbm-guidelines>

. This threshold for red cell transfusion (in the absence of blood loss due to bleeding) will be a Hb value of less than 80g/L.

All transfusion components in the U.K. and Australia, including red cells, are standardised and will conform to national specifications. All allogeneic blood components produced in the U.K. and Australia have been subjected to a pre-storage leucocyte filtration process.

No other medication changes are directed in this protocol, and standard care will otherwise be followed.

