#### 1.5.2 Primary efficacy outcomes

616 participants will be accrued to the UK/Australian clinical trial.

The participants will be randomised in a double blind fashion to receive TXA or a matching placebo.

The clinical trial will be conducted with the primary endpoint of decreased proportion of death or WHO Grade 2 or higher bleeding among all participants receiving TXA versus placebo over 30 days. The type 1 error will be controlled at a two-sided level of 0.05. The primary endpoint will be analysed using the Kaplan-Meier (KM) method to estimate the probability of bleeding or death within 30 days in the analysis populations. Power and sample size calculations are based on a log-rank test for comparing two survival curves, as described in Collett.

It is anticipated that the UK and Australia will be able to recruit 616 participants for this trial. Under the assumption that anti-fibrinolysis results in a decrease of death or WHO Grade 2 bleeding from 43% to 32%, the 616 participants will provide 80% power to detect an observed absolute decrease in bleeding rates of 11% (a relative reduction of 26% with a NNT of 8.9) and will be judged statistically significant at the two-sided 0.05 level. The planned trial size of 616 subjects includes an additional 5% of participants above the required sample size of 586. This 5% figure is more than the proportion of participants within TOPPS (4%) that dropped their platelet count below  $50 \times 10^9/L$  but did not drop their platelet below  $30 \times 10^9/L$ . This therefore accounts for the number of participants within the trial who are randomised but never receive the trial treatment.

We do not expect there to be a problem with the assessment of the primary outcome of bleeding over the 30 day trial period, starting from the first day of administration of the study intervention. In the recent TOPPS trial, completeness of bleeding outcome documentation was

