### 4.2 Analysis principles

Unless otherwise specified, all tests will be two-sided and p-values of less than 0.05 will be considered as evidence of a difference between treatment arms.

Multiple comparisons will be performed and this may increase the probability of observing a statistically significant result by chance. No adjustments will be made to account for multiple testing.

P-values will be reported to four decimal places with p-values less than 0.00005 as <0.0001. SAS or R will be used to conduct analyses.

All analyses will be adjusted for the stratification variable (recruitment site). Recruitment site will be accounted for by including a random effect in each model.

All hazard, odds and rate ratios will be presented as active treatment versus placebo. A ratio which is greater than 1 indicates that the hazard, odds or rate is greater in the active treatment arm. 95% confidence intervals will be presented with all ratios. P-values for regression models will be obtained by comparing  $-2 \times \log\text{-likelihood}$  values for models with and without the treatment term.

The key demographics and clinical condition of the participants at consent will be presented for each arm of the trial to describe the cohort. A CONSORT diagram will be presented to show how participants progressed through the trial.

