## Statistical Analysis Plan

---

unadjusted median, IQR number of red cell transfusions per day in hospital will be reported.

- Proportion of participants surviving up to 30 days without a platelet transfusion will be estimated by the Kaplan-Meier method and compared by treatment arm using Cox regression analysis. The event of interest is time to first platelet transfusion or death. Participants withdrawn or lost to follow up before day 30 will be censored at the time that they withdrew/were lost to follow up.
- Proportion of participants surviving up to 30 days without a red cell transfusion will be estimated by the Kaplan-Meier method and compared by treatment arm using Cox regression analysis. The event of interest is time to first red cell transfusion or death. Participants withdrawn or lost to follow up before day 30 will be censored at the time that they withdrew/were lost to follow up.
- Quality of life at study days 12 and 30 will be assessed using FACT-G and FACT-Th health questionnaires. For the FACT-G subscale scores (physical well-being, social/family well-being, emotional well-being, functional well-being), FACT-G total score and FACT-Th total score, mean (SD) will be calculated and compared by treatment arm using normal regression analysis. For each normal linear regression model, residual plots will be examined. If there is substantial evidence of skew or non-constant variance, log-transformed values will be used instead.

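### The two red cell transfusion outcomes could gain some precision, with no new data, by adjusting for haemoglobin at randomisation as well as site

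*SAP*

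**What the plan says.** SAP 4.2 sets the general rule: "All analyses will be adjusted for the stratification variable (recruitment site"), entered as a random effect in each model. Regression p-values come from comparing −2 log-likelihood with and without the treatment term. The footnote to the secondary efficacy table in SAP 5.5 repeats the rule: "All secondary efficacy outcome analyses are adjusted for centre".

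Two of the eight secondary efficacy outcomes concern red cells (SAP 2.2.1 and 4.4):

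- The number of transfusions per participant to day 30 uses a negative binomial model with an offset for days in hospital. The offset is an exposure term, not a baseline predictor.
- Survival to day 30 without a red cell transfusion uses Cox regression: "The event of interest is time to first red cell transfusion or death". No baseline covariate is named.

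Protocol 6.4.2 says that, in the absence of blood loss from bleeding, the red cell threshold "will be a Hb value of less than 80g/L". Hb is scheduled at consent, at randomisation and on Day 1 (Protocol Trial Schedule (Investigations); SAP Table 3). The baseline table in SAP 5.3 has a row "Haemoglobin at randomisation (G/L"). The only test that uses this value is the interim comparison of UK and Australian participants (SAP 4.1). No Hb-adjusted red cell analysis is planned, not even among the sensitivity analyses in SAP 4.7.

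**The concern.** If transfusion outside bleeding follows from crossing a fixed Hb level, a participant's starting distance from that level should help to determine when the first transfusion falls due, and how many follow, in either arm. Leaving a predictor of that kind out of the negative binomial model leaves its variation in the dispersion and widens the interval for the rate ratio. Leaving it out of the Cox model also pulls the hazard ratio towards 1. What is at stake is the precision of two secondary estimates. The covariate is already in the dataset.

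**Working it through.** **1. The plan's own figure.** SAP 1.5.2 assumes 43% versus 32% with the primary outcome, two-sided alpha 0.05 and 80% power, by a log-rank calculation.

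- Hazard ratio = ln(0.68)/ln(0.57) = 0.686.
- Events = 4 × (1.960 + 0.842)² / (ln 0.686)² = 221.2, so 222.
- Mean event proportion = (0.43 + 0.32)/2 = 0.375, so N = 222/0.375 = 592, against the stated 586.
- 586 × 1.05 = 615.3, so 616.

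The figure reproduces to about 1%, but it is for the primary outcome alone. The documents state no power for either red cell outcome.

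**2. What a given variance reduction is worth.** Suppose, as an assumption, that the site-only analysis had 80% power. With correlation r between Hb and outcome, the variance is multiplied by (1 − r²) and power becomes Φ(2.802/√(1 − r²) − 1.960).

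- r = 0.1, 0.2, 0.3, 0.4, 0.5 gives 80.4%, 81.6%, 83.6%, 86.4%, 89.9%.
- The gain is therefore negligible below r of about 0.2 and material from about 0.4.

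**3. Count model.** The large-sample variance of the log rate ratio is (1/μ₀ + k)/n + (1/μ₁ + k)/n. Assume n = 293 per arm, mean μ₀ = 5, rate ratio 0.81 (μ₁ = 4.05) and total dispersion k = 0.6. If Hb has log rate ratio b per SD, the residual dispersion is 1.6/exp(b²) − 1.

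- Without Hb: (0.800 + 0.847)/293 = 0.00562; power 80.3%.
- Hb rate ratio 0.90 per SD: residual k 0.584, variance ratio 1.020, power 81.0%.
- 0.82 per SD: residual k 0.537, variance ratio 1.082 (7.6% lower variance), power 83.3%.
- 0.74 per SD: residual k 0.462, variance ratio 1.201, power 86.9%.

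Simulating Hb falling to an 80 g/L trigger, rather than assuming b, gave 5% to 11% lower variance (robust Poisson, no offset). A further simulation usually gave about 4% to 12%, whether the drug acted on the Hb fall or only on bleeding-related transfusions. By step 2, 4% to 12% moves 80% power to 81.6% to 84.8%, equivalent to saving 586 × 0.04 = 23 to 586 × 0.12 = 70 participants.

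**4. Cox model.** The answer depends on how the drug acts.

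(a) *Drug acts on the whole transfusion hazard, Hb prognostic.* Assumed treatment hazard ratio 0.77, N = 586, 3,000 replicates, no site effect. Power without and with Hb:

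| Hb hazard ratio per SD | 30-day event probability 85% | 30-day event probability 70% |
|---|---|---|
| 1.00 | 81.1% / 80.7% | 72.7% / 73.0% |
| 0.82 | 79.0% / 81.0% | 70.6% / 71.6% |
| 0.67 | 73.2% / 80.2% | 66.2% / 73.5% |
| 0.55 | 64.8% / 80.1% | 59.2% / 70.3% |

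(b) *Drug slows the Hb fall by 20%.* Assumed Hb at randomisation mean 92 g/L (SD 8 to 12), change to day 1 SD 6 to 10, fall 2.0 g/L per day (SD 1.2), transfusion below 80. Stratifying by Hb band moved Cox power from 46% to 57%, 35% to 39% and 39% to 41% (500 trials each). A log-rank version with measurement SD 3 (1,000 trials each) moved it from 32% to 47%, 34% to 41% and 31% to 35%. The gains are 2 to 15 points.

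(c) *Drug acts only on bleeding-related transfusions.* Assumed 0.5% to 4% per day in the placebo arm, rate ratio 0.68, 400 trials per setting. Power without and with strata: 6/7, 5/4, 7/8, 5/5, 8/9, 10/10, 17/20, 24/23 percent. A separate run gave −1 to +0.4 points. In effect there is no gain.

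**5. Type I error.** With Hb-band strata it was 3.8% to 4.5% in one set of null simulations and 4.5% to 6.3% in another, where the unstratified test gave 4.6% to 6.3% (Monte Carlo standard error about 0.7 points). A linear Hb term with model-based standard errors gave 7.7% to 8.9% under the Hb-decline model, so strata are the safer form.

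**The case against.** The strongest case is that this is a choice rather than an error. Adjusting for the stratification variable is a conventional rule, clearly stated, and the resulting tests are valid. That stands.

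The size is also open to attack. Every Hb input is assumed. The Cox gain disappears if the drug works only through bleeding, and the 80 g/L threshold is explicitly for transfusion without bleeding-related blood loss. That stands too, and is why the range starts at no gain. The count model's gain does not depend on the mechanism in the same way.

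Hb at randomisation is not measured at the time origin: follow-up starts at first dose, and a transfusion can fall between randomisation and Day 1. This weakens the correlation; the simulations in step 4(b) allow for the change to day 1 but not for a transfusion in between. Day 1 Hb is closer, but the documents do not fix its timing relative to the first dose, and participants in the efficacy population who were never treated have no first-dose day. The randomisation value is the safer baseline.

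Finally, the simulations omitted the random site effect, and strata combined with that effect were not simulated.

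**Conclusion.** Both red cell models leave out a baseline value that is already collected and is likely to predict the outcome. The cost is some precision: about 4% to 12% of the variance of the log rate ratio for the count, and between nothing and roughly 2 to 15 power points for the Cox model, depending on how the drug acts. These ranges rest on the assumptions above; the documents cannot narrow them.

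A reader might infer three stronger things, none of which the documents support:

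- *That planned power is lost.* The statement that "the 616 participants will provide 80% power" refers to death or WHO grade 2 or higher bleeding. None is stated for red cells, and the primary analysis and the 616 are untouched.
- *That the planned tests are biased.* Attenuation of the Cox hazard ratio matters when there is an effect; the test of no effect remains valid.
- *That red cell saving is part of the trial's hypothesis.* Protocol 1.7 and the synopsis name bleeding and platelet demand, and the aim in SAP 1.1 names platelet use. Protocol 1.4 cites less red cell use in surgery and 1.6 mentions exposure to blood components generally, but red cell demand enters only as a secondary outcome.

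This is a minor improvement, not a flaw in the trial.

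**What to change.** Before unblinding, amend SAP 4.4 and the SAP 5.5 footnote:

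- **Count model:** add Hb at randomisation as a covariate, keeping the random site effect and the hospital-days offset.
- **Cox model for first red cell transfusion or death:** stratify by pre-specified bands of Hb at randomisation (for example 5 g/L bands from 80 to 105 g/L, with open ends), keeping the random site effect. The likelihood-ratio p-value in SAP 4.2 then still applies. A linear Hb term with robust variance is not proposed, because it would not fit that rule.
- **Missing values:** use Hb at consent where the randomisation value is missing; otherwise SAP 4.8 would drop those participants.
- **Footnote:** state that the red cell outcomes are also adjusted for, or stratified by, Hb at randomisation.

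The cost is SAP wording and one variable already in the dataset. The one downside is that the hazard ratio becomes conditional on baseline Hb; the site-only estimate can be reported alongside it.
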